5. MILESTONES

Milestone	Planned Date
Protocol/SAP (Version 1.0)	7 Dec 2023
Data collection started (Version 1.0)	2 Jan 2024
Data collection completed (Version 1.0)	3 Jan 2024
Final study tables (Version 1.0)	29 Jan 2024
Protocol/SAP (amendment V.1.)	23 Apr 2024
Final study tables (Phase V1.1)	30 April 2024
Final report	02 Dec 2024
Abstract 1	17 Feb 2024
Abstract 2	17 May 2024

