7. RESEARCH QUESTION AND OBJECTIVES

The objectives of this study are to 1) explore reliability of effect with acute use of rimegepant or triptans; 2) evaluate satisfaction with rimegepant or triptans; 3) evaluate willingness to continue using rimegepant or triptans; 4) explore proportion optimized on treatment with rimegepant or triptans.

Research questions:

1. What is the reliability of effect of rimegepant or triptans in the real world over multiple migraine attacks when taken PRN?
2. How satisfied are patients with rimegepant or triptans to treat their migraine attacks?
3. How willing are patients to continue taking rimegepant or triptans to treat their migraine attacks?
4. What proportion of those treating acutely with rimegepant or triptans are adequately responding and well managed?
5. When do patients administer rimegepant or triptans when treating an acute attack?

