Drivers for lack of satisfaction with current acute treatment (patient perspective)	Outcome-Objective 2	PSC HQ18b	It only reduces my migraine pain by half / IT reduces my migraine pain by less than half / It does not work quickly enough / It does not work as well as it used to / The number of side effects I experience / The severity of the side effects I experience / I am not happy with the way I have to take it / I find it difficult to know when to take it / I have too many different acute treatments to take / I worry about becoming dependent on it / It costs me too much money / Other
Patient willingness to continue use of acute treatment (patient perspective)	Outcome-Objective 3	PSC HQ18c	Definitely yes / Probably yes / Do not know / Probably not / Definitely not

Table 1. Variables

Variable	Purpose	Data Source(s)	Operational Definition
Migraine Treatment Optimization Questionnaire (m-TOQ6)	Outcome-Objective 4	PSC Section I- m-TOQ6	Reported by item and total score.
When patient takes acute Rx treatment	Outcome – Objective 5	PSC HQ3	Before any sign of a migraine attack, but in anticipation of one starting / At the first sign of a migraine attack (before the pain starts) / When the pain starts / After the pain has started and I have an idea of how severe it is
How many days per month patient takes acute Rx treatment	Outcome – Objective 5	PSC HQ4a	

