8.6. Data Analysis

Analyses will be based on patients receiving rimegepant or triptans only as an acute treatment currently for their migraine.

Data will be stratified by time spent on rimegepant or triptans and number of migraine related headache days.

Analysis will be descriptive. The mean, standard deviation (SD), median, 25th and 75th percentiles and minimum and maximum values will be reported for numeric variables, whilst relative frequencies and percentages will be reported for categorical variables.

The real-world nature of the DSP means many variables will contain missing data. We would expect the base of patients to vary from variable to variable due to imperfect physician knowledge, physicians not wishing to answer the question, etc. The base relevant to each analysis will be reported in any data tables provided. There will be no imputation of missing data. Where missing values are found in a particular variable, any patients with missing values will be removed from all pieces of analysis where that variable is used. However, patients removed from one piece of analysis are still eligible for inclusion in other analyses. In the derivation of PRO variables, the handling of missing data will follow the official instructions as provided by the author/owner of the PRO questionnaire.

Detailed methodology for summary and statistical analyses of data collected in this study is documented in a statistical analysis plan (SAP) below:

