Satisfaction with current acute treatment (patient perspective)	PSC HQ18a	
Proportion of responses to: Extremely satisfied / Satisfied / Slightly Satisfied / Neither satisfied nor dissatisfied / Slightly dissatisfied / Dissatisfied / Extremely dissatisfied
 
Satisfaction will be defined as responses to: 'Extremely satisfied' or 'Satisfied' or 'Slightly Satisfied' combined
 
Dissatisfaction will be defined as responses to: 'Neither satisfied nor dissatisfied' or 'Slightly dissatisfied' or 'Dissatisfied' or 'Extremely dissatisfied' combined
 
Data to be matched to PRF equivalent data (PRF IQ1a)

Drivers for lack of satisfaction with current acute treatment (patient perspective)	PSC HQ18b	
Proportion of responses to: It only reduces my migraine pain by half / It reduces my migraine pain by less than half / It does not work quickly enough / It does not work as well as it used to / The number of side effects I experience / The severity of the side effects I experience / I am not happy with the way I have to take it / I find it difficult to know when to take it / I have too many different acute treatments to take / I worry about becoming dependent on it / It costs me too much money / Other

8.6.4. Analysis for Objective 3

Objective 3 focuses on willingness of patients to continue taking rimegepant or triptans to treat their migraine attacks. This will be addressed by describing the following:

Variable	Data Source(s)	Analysis Plan
Patient willingness to continue use of acute treatment (patient perspective)	PSC HQ18c	
Proportion of responses to: Definitely yes / Probably yes / Do not know / Probably not / Definitely not
 
Responses of "Don't know" will be omitted from analysis.
 
Willingness to continue will be defined as responses to: 'Definitely yes' or 'Probably yes' combined
 
Unwillingness to continue will be defined as responses to 'Probably not' and 'Definitely not' combined

8.6.5. Analysis for Objective 4

Objective 4 focuses on the proportion of those treating acutely with rimegepant or triptans that are optimised on their treatment. This will be addressed by describing the following:

Variable	Data Source(s)	Analysis Plan
Migraine Treatment Optimization Questionnaire (m-TOQ6)	PSC Section I- m-TOQ6	Reported by proportion of responses per time item and total score. The official m-TOQ6 scoring algorithm will be used to calculate total score.

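### Objective 3 drops the *Do not know* answers on willingness to continue, so the percentage describes only patients who gave a yes or no answer

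*Combined protocol and SAP*

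**What the plan says.** Research question 3 (Section 7) asks "How willing are patients to continue taking rimegepant or triptans to treat their migraine attacks". One variable serves it: PSC HQ18c, completed by the patient. Table 1 in Section 8.3 gives its response options as "Definitely yes / Probably yes / Do not know / Probably not / Definitely not".

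The HQ18c cell in Section 8.6.4 contains three instructions:

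- Tabulate "Proportion of responses to: Definitely yes / Probably yes / Do not know / Probably not / Definitely not".
- Then, for *Don't know* responses: they "will be omitted from analysis".
- Combine the two yes options as willing and the two not options as unwilling. *Do not know* belongs to neither group.

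Section 8.6 adds two rules that bear on this: "Data will be stratified by time spent on rimegepant or triptans and number of migraine related headache days" and "The base relevant to each analysis will be reported in any data tables provided". It also rules out imputation of missing data. No section describes an analysis that keeps the *Do not know* answers.

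**The concern.** The cell lists a category for reporting and then removes it. HQ18c has only one such option, so *Do not know* and *Don't know* must be the same answer despite the different wording.

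The larger issue is the denominator. Once the answer is omitted, the result is willingness among patients who have made up their minds, which is narrower than the research question. Nothing else under Objective 3 would show how many patients were undecided.

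Amendment 1 added triptans so that the two groups can be described against each other. If the undecided share differs between them, the side-by-side percentages can differ, or agree, for reasons unrelated to willingness. The rimegepant group has at most 29 patients before stratification, so a few answers move its percentage appreciably.

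**Working it through.** **Is *Do not know* an answer or a missing value?** Every other rule in the SAP that drops *Don't know* applies to a physician-completed item: employment (AQ8, AQ9, AQ10), insurance (AQ14), symptoms (CQ6a, CQ6b), attack duration (CQ10), time on treatment (DQ2a) and failure to reach pain freedom (DQ18). On those items it plausibly means that the physician lacks the information. HQ18c is the only patient-completed item with such a rule; HQ3, HQ4a, HQ6, HQ18a and HQ18b have none. It asks patients about their own intention and places *Do not know* between *Probably yes* and *Probably not*. The natural reading is undecided. This is inferred from the item and the option order, not stated.

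**Inputs.** Section 8.5 gives 29 rimegepant and 113 triptan patients for patient-reported outcomes. (These add to 142 and the section states 143; the difference does not affect this point.) They are upper limits for HQ18c, since some patients may have left it blank. The plan states no willingness figure, so there is none to reproduce. The *Do not know* share d and the willing share p are **assumed** throughout.

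**Formula.** Let p be the willing share among all who answered.

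- Reported willing = p / (1 − d)
- Reported unwilling = (1 − p − d) / (1 − d)

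Both shares are multiplied by 1/(1 − d), so their ratio does not change and neither can fall.

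**Size at an assumed p = 65%.**

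| d | Willing, all answers | Willing, as reported | Unwilling, all answers | Unwilling, as reported |
|---|---|---|---|---|
| 0% | 65% | 65.0% | 35% | 35.0% |
| 5% | 65% | 0.65/0.95 = 68.4% | 30% | 0.30/0.95 = 31.6% |
| 10% | 65% | 0.65/0.90 = 72.2% | 25% | 0.25/0.90 = 27.8% |
| 20% | 65% | 0.65/0.80 = 81.3% | 15% | 0.15/0.80 = 18.8% |

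**Effect of the first undecided patient.** With p × n willing patients, the base falls from n to n − 1, so the reported figure rises by p/(n − 1).

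- Rimegepant, n = 29: 0.60/28 = 2.1 points to 0.80/28 = 2.9 points
- Triptans, n = 113: 0.60/112 = 0.5 points to 0.80/112 = 0.7 points

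**Hypothetical contrast.** Take 20/29 and 78/113 willing, both 69.0%.

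| Undecided (rimegepant, triptans) | Rimegepant as reported | Triptans as reported | Apparent gap |
|---|---|---|---|
| 5 (17%), 6 (5%) | 20/24 = 83.3% | 78/107 = 72.9% | +10.4 points |
| 1 (3%), 20 (18%) | 20/28 = 71.4% | 78/93 = 83.9% | −12.4 points |

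The gap comes entirely from the undecided counts and can favour either group.

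**The case against.** The strongest reply is that the cell can be executed and the rule is disclosed. The SAP elsewhere lists an option and then drops it, for example *None* under comorbidities and *No drug treatment* under prior treatments. Read that way, the list gives the response options and the next sentence gives the rule. This stands as far as it goes: the wording is untidy rather than unworkable. But that reading confirms the restricted denominator. If instead all five categories were tabulated and *Do not know* left out only of the summary, the headline percentage would still exclude the undecided.

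Other points limit the supporting arguments:

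- Table 1 states no omission rule for any variable, so its silence on HQ18c is not evidence of intent.
- DQ18, an Objective 1 outcome, also loses its *Don't know* answers, so the practice is not confined to background facts. It is physician-answered, however.
- Objective 2 keeps its neutral answer in the base but counts it on the negative side: "Dissatisfaction will be defined as responses to: 'Neither satisfied nor dissatisfied". It shows that a middle answer was retained for a neighbouring patient question; it is no precedent for a separate undecided group.
- The questionnaire itself is not in the text, so the undecided reading cannot be checked.
- The contrast above needs clearly unequal undecided shares, and nothing in the documents suggests them. Sampling error is also large: a 95% Wilson interval for 20/29 runs from 50.8% to 82.7%.

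Reporting the base would show that the denominator shrank. It would not correct the percentage or separate undecided answers from blanks. Nor does the descriptive purpose make the point harmless: here the reported proportion is the result.

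**Conclusion.** The concern holds. As written, the only Objective 3 result is calculated among patients who gave a yes or no answer, while the research question concerns patients without that restriction. Both the willing and the unwilling percentages can only rise or stay the same, by the factor 1/(1 − d).

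The text and the arithmetic are certain; the size is not. It could be nil, or about 3 to 16 points at the assumed 65% willing with 5% to 20% undecided. Any distortion of the comparison depends on both the undecided shares and the willingness level in each group, and no direction can be predicted. The conclusion assumes that *Do not know* is a real answer and not non-response. This should be fixed before the willingness figures are relied on.

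**What to change.** In Section 8.6.4, delete the omission sentence for HQ18c. Then specify:

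- all five response categories, with counts and percentages, for each treatment group;
- three summary groups: willing (*Definitely yes* or *Probably yes*), undecided (*Do not know*) and unwilling (*Probably not* or *Definitely not*);
- everyone who answered HQ18c as the base, overall and within the planned strata, with blanks counted separately;
- if wanted, willingness among decided patients as a secondary result labelled as such.

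The change is to one cell and uses data already collected. The Objective 3 tables must be re-run, including the strata by time on treatment and headache days. If the Version 1.0 tables (planned for 29 Jan 2024) or either abstract used the same rule, those figures need re-running too; the documents do not show whether they did. The price is a willingness percentage that may be lower, by an amount that depends on d.

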8.7. Quality Control

This study will be conducted according to ARW's standard operating procedures, with the results of the analysis checked for validity and consistency.

8.8. Limitations of the Research Methods

- Physicians are asked to provide data on consecutively consulting patients who meet the eligibility criteria, thus reducing the chance of any selection bias on the consulting population by physicians. However, generalisability of the study results to the wider patient population will be impacted as follows:
 - Participants from the Migraine VII DSP (from which the study population is drawn) do not constitute a true random sample, more a pragmatic (physicians) and pseudo-random (patients) sample, and although minimal selection criteria were imposed to identify physicians for inclusion, participation is influenced by the willingness to complete the record forms.
 - The patient sample may be more severely affected by their disease and/or treatment due to their consulting nature (ie, a requirement for inclusion in the Migraine VII DSP). Furthermore, patients who consult more frequently are more likely to be included in the patient sample. However, physicians were asked to provide data for a number of consecutively consulting patients meeting the Migraine VII DSP inclusion criteria to reduce selection bias.

- No patient selection verification procedures were applied to the Migraine VII DSP, and identification of the participants included was based on physician judgement/ perception rather than formal medical coding (eg, diagnostic codes). Nevertheless, this process is representative of physicians' real-world classification of their patients.
- The cross-sectional design of the DSP does not allow for causal relationships; however, identification of associations is possible.
- Physicians and patients were requested to capture patient information retrospectively within the PRF and PSC respectively, which may introduce recall bias – a common limitation of survey data. However, physicians did have the ability to refer to the patients' medical records while completing the PRF, thus minimising the possibility of recall bias. Moreover, most questions within the PSC have a limited recall period to further minimise the risk of recall bias.

Study data are self-reported by participants (eg, physicians and patients) as no independent verification was possible due to the nature of the ARW DSP methodology.

8.9. Other Aspects

Strengths of this research methods are:

- Dataset provides the physicians' actual treatment and prescribing decisions.
- The DSP is a pseudo-random sample. The methodology used (collecting next n consulting patients) aims to reduce the likelihood of selection bias, and the sample should be representative of the consulting population.
- The dataset is an independent data source providing impartiality of data reporting with no set hypotheses at design stage.
- The DSP includes all consulting patients, covering both insured and non-insured patients. Each patient is unique and there is no double-representation.
- Amongst the variables collected, importantly, the DSP specifically includes, via the physician-completed record form, clinical characteristics, the patient's complete treatment history from diagnosis to current day and reasons for prescribing / stopping treatment.

9. PROTECTION OF HUMAN PARTICIPANTS

9.1. Patient Information and Consent

This study is an analysis of secondary data from the Migraine VII DSP. Participating patients in the Migraine VII DSP were treated in accordance with usual medical practice; no additional assessments or tests were conducted in order to participate. Data were collected cross-sectionally at a single point in time and retrospectively for historical information. Patients provided their informed consent prior to completion of the PSC and did not provide any personally identifiable information.

9.2. Ethical Conduct of the Study

The study will be conducted in accordance with legal and regulatory requirements, as well as with scientific purpose, value and rigor and follow generally accepted research practices.

The DSP was performed in compliance with the EphMRA Code of Conduct and ARW standard operating procedures.

The Migraine VII DSP was submitted to the Pearl IRB in the US (IRB number: 22-ADRW-143). All data were deidentified and pseudoanonymised.

All study results will be in tabular form and aggregate analyses. As this is an analysis of secondary data, additional informed consent, ethics committee or IRB approval are not required. Any publications and reports will not include subject identifiers.

10. MANAGEMENT AND REPORTING OF ADVERSE EVENTS/ADVERSE REACTIONS

This is a database analysis study based on secondary use of data collected for other purposes. No administration of any therapeutic or prophylactic agent was required in this protocol. No reporting of individual case safety reports (ICSRs) ie, adverse events or product quality complaints, to regulatory agencies are required for this database study, as there is no access to individual patient/subject records, it is not possible to assess the causality.

This study involves data that exist as structured data by the time of study start.

In these data sources, individual patient data are not retrieved or validated, and it is not possible to link (ie, identify a potential association between) a particular product and medical event for any individual. Thus, the *minimum criteria for reporting an adverse event (AE) (ie, identifiable patient, identifiable reporter, a suspect product, and event) cannot be met.*

11. PLANS FOR DISSEMINATING AND COMMUNICATING STUDY RESULTS

A final study report will be prepared describing methods, results, and interpretation of results upon completion of the study (anticipated Q1 2024).

Study results are also intended to be submitted for consideration at a scientific congress and published in a peer-reviewed journal (target congress and journal to be determined).

Authorship of any publications resulting from this study will be determined on the basis of the International Committee of Medical Journal Editors (ICJME) Recommendations for the Conduct, Reporting, Editing and Publication of Scholarly Work in Medical Journals.²³

In the event of any prohibition or restriction imposed (eg, clinical hold) by an applicable competent authority in any area of the world, or if the party responsible for collecting data from the participant is aware of any new information which might influence the evaluation of the benefits and risks of a Pfizer product, Pfizer should be informed immediately.

